2.4 POOLING OF CENTERS

Data of all sites will be pooled together for analysis.

2.5 HANDLING OF MISSING DATA

Unless otherwise specified, missing data will not be imputed. All analyses will be based on available data.

2.6 ANALYSIS SOFTWARE

All summaries and statistical analyses will be generated using SAS® version 9.2 or later.

3. STUDY SUBJECTS

3.1 DISPOSITION OF SUBJECTS

Disposition will be summarized by cohort and overall in all enrolled subjects.

The disposition will include the following:

- Subjects enrolled
- Subjects in the Safety Population
- Subjects in the MITT Population
- Subjects in the PP Population
- Subjects who completed the period
- Subjects who discontinued study drug before the end of the period
- Reasons for study drug discontinuation

For the 26-week open-label treatment period, completing subjects are those completing the 26-week open-label treatment period, regardless of whether they entered the 52-week OLE.

Likewise, for the 52-week OLE period, completing subjects are those completing the 52 week OLE period, regardless of whether they continued beyond the extension period. A listing of dispositions will be provided for all subjects.

3.2 PROTOCOL DEVIATIONS

The clinical team will identify deviations and the deviations will be recorded into the database. A subject data listing will be provided.

4. DEMOGRAPHICS AND BASELINE CHARACTERISTICS

4.1 DEMOGRAPHICS AND BASELINE CHARACTERISTICS

Demographic data (age, gender, race, and ethnicity) and baseline characteristics (including height and weight) collected at study screening and derived BMI will be summarized using descriptive statistics by cohort and overall in the safety population, MITT population and PP population if they differ.

Height (in cm) = Height (in inches) * 2.54

Weight (in kg) = Weight (in lbs) * 0.4536

BMI (kg/m²) = Weight (kg)/[Height(m)²]

A subject data listing of demographics and baseline characteristics will be provided.

4.2 MEDICAL HISTORY

Medical history will be coded with the Medical Dictionary for Regulatory Activities (MedDRA) Terminology version 16.0. The number and percent of subjects with clinically significant medical history at screening will be summarized by system organ class (SOC) and Preferred Term by cohort and overall in safety population.

5. PRIOR AND CONCOMITANT MEDICATIONS

Prior medications are defined as medications that started and stopped prior to the first dose of study drug. Concomitant medications are defined as medications (other than the study drug) taken on or after the first dose of the study drug during the study, regardless of when they were first taken. The summary of concomitant medications for the main 26-week open-label treatment period of the study will not include concomitant medications that start after the main 26-week open-label treatment period of the study; i.e. they will not include any concomitant medications starting on or after the first dosing day of the OLE period.

All investigator terms for medications recorded on the CRF will be coded using the World Health Organization (WHO) Anatomical Therapeutic Chemical (ATC) drug dictionary (Version WHO Drug Dictionary, March 2014). The number (percentage) of subjects who took prior and concomitant medications will be summarized by cohort and overall in the safety population, by ATC Classification and WHO Drug Preferred Term. Prior and concomitant Non AEDs and AEDs will be summarized separately.

A subject data listing of prior and concomitant medications will be provided, separately for non-AED and AEDs.

To define prior or concomitant medication, the following table describes how missing date information will be handled:

Partial Missing Start or Stop Date	Imputed Start Date	Imputed Stop Date
Missing year, month, and day	First dose date	
Missing month and day, and the year is present	First dose date if the year is the same as the year of first dose date, else first dose date of the OLE if the year is the same as the year of the first OLE dose date, else January 1 of the medication start year.	December 31 of that year
Missing day, but year and month are present	First dose date if the year and month are the same as the year and month of first dose date, else first dose date of the OLE if the year and month are the same as the year and month of the first OLE dose date, else the 1 st of the medication start month.	Last day of that month
Missing month, but year and day are present	Assume day is also missing and impute as above	Missing month imputed as December

If an imputed start date is later than the stop date, then the stop date (after any needed imputations) will be used instead for the imputed start date.

6. EFFICACY ANALYSES

All efficacy analyses will be summarized by cohort in the MITT population. These summaries will include only the CDKL5, LGS, and PCDH19 cohorts since only 2 patients were enrolled in the CWS cohort. However, the CWS cohort will be included in the subject data listings. For the analyses of seizures and clusters, the baseline period consists of up to 12 weeks before the first day of treatment, and the 26-week open-label treatment period starts with the day following the first day of treatment until the final visit for subjects who do not enter the OLE and up to the day before the first dose of OLE treatment for those who do. The first day of treatment is not in either period since the times of seizures were not collected.

Seizure diary compliance will be summarized by cohort. The calculated compliance is:
 $100 \times (\text{Number of Days with Available Seizure or Cluster Diary}) / (\text{Last Available Seizure or Cluster Diary Date} - \text{First Available Seizure or Cluster Diary Date} + 1)$.

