9.3.2 Inclusion Criteria

- 1. Have parent or legal guardian available and willing to give written informed consent, after being properly informed of the nature and risks of the study and prior to engaging in any study-related procedures.
- 2. Outpatients between 2 and 18 years of age at time of consent.

3. In the opinion of the investigator have confirmed PCDH19 genetic mutation, confirmed CDKL5 genetic mutation or Dravet Syndrome confirmed by a SCN1A mutation, or genetic epilepsy testing confirming a LGS or CSWS condition associated with this genetic phenotype. Refractive cases of LGS or CSWS that remain idiopathic or have prior history of steroid or ACTH response can also be entered if documentation confirms specific genetic defects are not found and prior steroid response clinically occurred.

4. Seizure criteria:

- a. Have uncontrolled cluster seizures (3 or more seizures over the course of 12 hours) every 6 weeks or less during baseline, or bouts of status epilepticus on intermittent basis, or
- b. Have uncontrolled non-clustered seizures (focal dyscognitive, focal convulsive, atypical absences, hemiclonic seizures, spasms, or tonic-spasm seizures) with a frequency ≥4 seizures per 28-day period during baseline, or
- c. Have ≥4 generalized convulsive (tonic-clonic, tonic, clonic, atonic seizures) per 28-day baseline period during baseline, or
- d. Have subclinical CSWS syndrome with or without clinical events on EEG
- 5. Subjects should be on a stable regimen of AED medication, and generally in good health.
- 6. Parent or guardian is able and willing to maintain an accurate and complete daily written seizure calendar for the duration of the study.
- 7. Able and willing to take study medication with food, two or three times daily. Ganaxolone must be administered with food.

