9.5 Efficacy and Safety Variables

9.5.1 Calculation of Baseline

Baseline will be calculated from a maximum of 12 weeks' of seizure calendar data with a minimum of 4 weeks of data required, which should include contiguous retrospective ratings provided after signing informed consent. Acceptable retrospective daily seizure

data include a diary record of the frequency and type of seizures by day. Source data may include a seizure diary or calendar, recorded data from smart phones or other devices. Seizure clusters are to be identified, and the number of seizures in the daily cluster should be counted or given as best estimate.

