2.2.2 Modified Intention-To-Treat Population (MITT)

The MITT population includes all subjects who entered into the study and received at least 1 dose of study drug and provided at least 1 day of post-baseline seizure calendar data. This is the primary population for the efficacy analyses.

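### The diary compliance formula stops counting at the child's own last diary entry, so treatment days missing after that entry never count as missed

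*SAP*

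**What the plan says.** SAP section 6 introduces the measure with "Seizure diary compliance will be summarized by cohort. The calculated compliance is". The numerator is the "Number of Days with Available Seizure or Cluster Diary". The denominator is the "Last Available Seizure or Cluster Diary Date" minus the "First Available Seizure or Cluster Diary Date", plus 1. No period is named, and no threshold is attached to the result.

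The paragraph just before the formula defines the two seizure-analysis periods. Baseline is up to 12 weeks before the first day of treatment. For children who do not enter the OLE, "the 26-week open-label treatment period starts with the day following the first day of treatment until the final visit"; for those who do, the period ends the day before the first OLE dose. The first treatment day belongs to neither period.

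Four other provisions bear on the point:

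- Protocol 9.3.2 requires a parent or guardian who is "able and willing to maintain an accurate and complete daily written seizure calendar for the duration of the study".
- Protocol 9.5.1 sets the baseline length: "Baseline will be calculated from a maximum of 12 weeks' of seizure calendar data with a minimum of 4 weeks of data required".
- SAP 2.2.2 admits to the primary efficacy population any child who took a dose and "provided at least 1 day of post-baseline seizure calendar data".
- SAP 6.1 divides the seizure count by days with available data, and SAP 2.5 imputes nothing.

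**The concern.** A completeness measure should compare the days recorded with the days that ought to have been recorded. Here both ends of the denominator come from the diary being checked. Once a caregiver stops recording for good, the denominator stops growing as well, and the remaining treatment days drop out of the calculation.

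This matters because the rest of the plan relies on available days. A 28-day rate built on a handful of early treatment days is still reported as the rate for the 26-week period, and a single post-baseline diary day is enough to enter the primary population. The per-protocol definition in SAP 2.2.3 asks for 6 weeks of study drug but sets no diary minimum. Disposition (SAP 3.1) counts discontinuation of study drug, not of the diary. A child who stays on drug to week 26 while the diary stops early would therefore appear as a completer with full compliance.

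Other results need the same information. The longest seizure-free run in SAP 6.2.8 is a percentage of available days. The months 1 to 3 analysis in SAP 6.3 can be set against the 26-week result only if the reader knows how many children have diary data after Day 91. With up to 10 children planned per cohort (SAP 1.3.3), one or two such children can matter.

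**Working it through.** The documents state no compliance figure to reproduce, so the formula is applied directly.

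**Inputs**

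- Baseline diary: 28 or 84 days (4 to 12 weeks, Protocol 9.5.1).
- Treatment period for seizure analyses: Study Day 2 to the final visit (SAP 6). Taking 26 weeks as 182 days (an assumption), this is Days 2 to 182, or 181 days.
- Diary assumed daily, including Day 1, except where a gap or stop is stated.

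**Formulas**

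- SAP: 100 × diary days / (last diary date − first diary date + 1).
- Treatment completeness: 100 × diary days on Days 2 to 182 / 181.

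**Case 1: the diary stops for good and the child stays on drug.** Take 84 baseline days, Day 1 and 10 treatment days.

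- SAP formula: (84 + 1 + 10) / (84 + 1 + 10) = 95/95 = 100%.
- Treatment completeness: 10/181 = 5.5%.

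Other stopping days, for either baseline length:

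| Last diary day | SAP formula | Treatment completeness |
|---|---|---|
| Day 2 | 100% | 1/181 = 0.6% |
| Day 15 | 100% | 14/181 = 7.7% |
| Day 29 | 100% | 28/181 = 15.5% |
| Day 57 | 100% | 56/181 = 30.9% |
| Day 91 | 100% | 90/181 = 49.7% |

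Restricting the SAP formula to treatment days, still on the child's own dates, gives the same 100%; for the Day 29 stop it is 28/28. The own-date span causes the failure, not any pooling of periods.

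**Case 2: gaps inside a diary that runs to Day 182.** The SAP column assumes baseline and treatment are pooled, so the span is 28 + 182 = 210 or 84 + 182 = 266 days.

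| Treatment days missing | SAP, 28-day baseline | SAP, 84-day baseline | Treatment completeness |
|---|---|---|---|
| 28 | 182/210 = 86.7% | 238/266 = 89.5% | 153/181 = 84.5% |
| 60 | 150/210 = 71.4% | 206/266 = 77.4% | 121/181 = 66.9% |
| 90 | 120/210 = 57.1% | 176/266 = 66.2% | 91/181 = 50.3% |
| 150 | 60/210 = 28.6% | 116/266 = 43.6% | 31/181 = 17.1% |

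Interior gaps are detected. If the periods are pooled, a 60-day gap is understated by 71.4 − 66.9 = 4.5 to 77.4 − 66.9 = 10.5 points.

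**The case against.** The strongest reply is that the failure needs an unusual child. For a child who stops drug and leaves, Protocol 9.3.4.2 has the remaining calendars handed in at termination, so the last diary date should lie close to the final visit and the SAP figure is then nearly right. A child who stays on drug without a diary would have to pass calendar review at Visits 3 to 7, and Protocol 9.4.9 allows removal for calendar non-compliance. Subject listings (SAP 2.1 and 6.1) and the deviation listing (SAP 3.2) are practical to read at this sample size. Compliance enters no endpoint, population or imputation rule.

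Much of this stands, and it limits how often the problem would arise and what it would affect. It does not make the figure correct for the child in question. Removal is discretionary, disposition tracks the drug, and the SAP does not say that any listing will set diary days against expected days.

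A reader might also infer more than the documents support:

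- **That the measure is blind to all missing treatment data.** It is not; Case 2 shows that interior gaps lower it.
- **That the SAP pools the two periods.** The formula has no period term, so pooling is the natural reading, but the SAP does not say so. SAP 2.1 promises separate tables for each portion of the study while carrying baseline information into all of them.
- **That days before the first entry are wrongly ignored.** Baseline length varies by design from 4 to 12 weeks, so there is no fixed start date against which earlier days could be missed.
- **That whole cohorts stopped recording.** Nothing in the documents shows how often, or whether, diaries stopped early.

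**Conclusion.** The point holds for treatment days missing after the last diary entry. The stated rule gives 100% for a daily diary that stops at any day, against 5.5% of treatment days in the worked example and 0.6% to 49.7% for stops between Day 2 and Day 91. The missing period label is a lesser fault: if the periods are pooled, interior gaps are diluted but still visible.

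These figures rest on 26 weeks being 182 days, daily recording up to the stop, and a child who remains in the treatment period to Day 182. The fault lies in the reporting of completeness. It does not bias any efficacy estimate, but no other planned summary would tell the reader how much of the 26 weeks those estimates cover. It should be corrected.

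**What to change.** Replace the single formula in SAP section 6 with two figures per child, using the period bounds that section already contains:

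- **Treatment:** diary days from Study Day 2 onward in the period, divided by all days from Study Day 2 to the final visit, or to the day before the first OLE dose for children who continue. A child who withdraws and attends a final visit is not penalised for later days.
- **Baseline:** diary days, divided by days from the first baseline diary date to the day before the first dose. This respects the variable baseline length.

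Summarise both by cohort and show the number of treatment diary days for each child. No compliance cut-off is needed; the documents give no basis for one.

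No new data are required and no efficacy result changes. The cost is one changed formula, an extra row in a planned table, and a compliance figure that may look less favourable.

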6.1 PRIMARY EFFICACY ANALYSIS

The primary efficacy endpoint is the percent change in 28-day total seizure frequency in the 26-week open-label treatment period relative to the baseline in the MITT population. Frequency of total seizures includes all seizure subtypes presented as individual seizures or clusters. Post-baseline 28-day total seizure frequency will be calculated as the total number of individual seizures and clusters in the 26-week open-label treatment period divided by the number of days with available seizure/cluster data in the period, multiplied by 28. Baseline 28-day total seizure

frequency will be calculated as the total number of individual seizures and clusters in the baseline period divided by the number of days with available seizure/cluster count data in the period, multiplied by 28. The calculation for percent change from baseline in 28-day total seizure frequency will be done as follows for each subject:

$$\left(\frac{[(\text{Post-baseline 28-day seizure frequency}) - (\text{Baseline 28-day seizure frequency})]}{(\text{Baseline 28-day seizure frequency})} \right) \times 100\%$$

The baseline and post-baseline values and the arithmetic and percent changes from baseline in 28-day total seizure frequency will be summarized by cohort separately using descriptive statistics in the MITT population and PP population if they differ. A subject data listing will be provided.

6.2 SECONDARY EFFICACY ANALYSIS

6.2.1 Percent Change in Individual Seizure Frequency per 28-day Period from Baseline

Baseline and post-baseline values and arithmetic and percent changes in 28-day individual seizure frequency will be calculated in the same way as the primary efficacy endpoint but only individual seizures (not clusters) will be considered. Summary statistics will be presented by cohort separately using descriptive statistics. A subject data listing will be provided.

6.2.2 Percent Change in Cluster Frequency per 28-day Period from Baseline

Post-baseline 28-day cluster frequency will be calculated as the total number of clusters in the 26-week open-label treatment period divided by the number of days with available cluster count data in the period, multiplied by 28. Baseline 28-day cluster frequency will be calculated as the total number of clusters in the baseline period divided by the number of days with available cluster count data in the period, multiplied by 28. The percent change from baseline in 28-day cluster frequency will be calculated as (post-baseline 28-day cluster frequency minus baseline 28-day seizure frequency) divided by baseline 28-day cluster frequency, multiplied by 100%. (If on a given day seizure data are available then if no cluster data are available the cluster count for that day will be considered as zero. This is done since parents/caregivers often did not record the cluster information if there were no seizures.)

Summary statistics for the baseline and post-baseline values and the arithmetic and percent changes will be presented by cohort separately using descriptive statistics. A subject data listing will be provided.

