Protocadherin (PCDH)19- female-pediatric epilepsy (FPE), also known as PCDH19 female-limited epilepsy (FLE) or epilepsy in females with mental retardation (EFMR), is a serious epileptic syndrome characterized by early-onset cluster seizures, cognitive and sensory impairment of varying degrees, and behavioral disturbances in some individuals.¹ This disorder is associated with a mutation of the PCDH19 gene, the gene that encodes for protocadherin19 on the X chromosome.^{2,3} The mechanism by which this mutation contributes to the development of epilepsy and intellectual impairment is not fully understood, however protocadherin19 is a transmembrane protein of calcium-dependent cell-cell adhesion molecules that is strongly expressed in neural tissue (e.g., hippocampus, cerebral cortex, thalamus, amygdale), and which appears to be related to synaptic transmission and formation of synaptic connections during brain development.³ Research suggests impairment of GABAergic signaling both at the agonist and receptor levels is present in girls with PCDH19 mutations and pediatric-onset epilepsy.⁴

The hallmark characteristics of PCDH19-FPE are clusters of seizures which start in infancy or early childhood often associated with fever or immunization.⁵⁻⁷ Patients with PCDH19-FPE may experience individual seizures in addition to clusters and multiple seizure types. In some patients, seizures improve as patients reach puberty, possibly due to increased endogenous levels of progesterone and allopregnanolone.⁸⁻¹⁰

Background on CDKL5 Disorder

CDKL5 disorder or CDKL5 stands for cyclin dependent kinase like 5, and is located on the X chromosome. The CDKL5 gene was previously called STK9. CDKL5 is a rare X linked genetic disorder that results in early onset, difficult to control seizures, and severe neuro-developmental impairment. ¹⁹

Most of the children affected by CDKL5 present with irritability in the perinatal period, early epilepsy, hand stereotypies, severely impaired psychomotor development and severe hypotonia. In contrast to classical Rett syndrome they also may have absence of a classic regression period, poor eye contact, generally normal head circumference and other growth parameters and relative absence of autonomic dysfunction. ¹⁹

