1.2.2 Secondary Efficacy Endpoints

Secondary efficacy endpoints include:

1. Percent change in individual seizure frequency per 28-day period from baseline
2. Percent change in cluster frequency per 28-day period from baseline
3. Percent change in the average number of seizures per cluster from baseline
4. Percent change in total seizure frequency (individual seizures and clusters) per 28-day period from baseline per seizure subtype
5. Change in the percentage of individual seizure and cluster free days from baseline
6. Change in the percentage of individual seizure free days from baseline
7. Change in the percentage of cluster free days from baseline
8. Change in the longest period of time individual seizure and cluster free (% relative to number of days with seizure data) from baseline
9. Proportion of subjects with $\geq 25\%$, 50% , or 75% reduction in 28-day total seizure frequency (sum of individual seizures and clusters) compared with baseline

10. The Clinical Global Impression of Improvement: Clinician (CGII-C)
11. Clinical Global Impression of Improvement: Patient/Caregiver (CGII-P)

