6.2.6 Change in the Percentage of Individual Seizure Free Days from Baseline

Post-baseline percentage of individual seizure free days will be calculated as the number of individual seizure free days in the 26-week open-label treatment period divided by the number of days with available individual seizure occurrence data in the period and multiplied by 100.

Baseline percentage of individual seizure free days will be calculated as the number of individual seizure free days in the baseline period divided by the number of days with available individual seizure or cluster data in the baseline period, multiplied by 100.

Baseline and post-baseline values and arithmetic changes from baseline in seizure free days will be summarized by cohort separately using descriptive statistics. A subject data listing will be provided.

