6.2.10 CGII-C and CGII-P

Clinical Global Impression of Improvement –Clinician (CGII-C), or Clinical Global Impression of Improvement –Patient/Caregiver (CGII-P): A 7-point Likert scale completed by the Clinician

or Patient/Caregiver representing the degree to which the subject's epilepsy symptoms have changed relative to baseline. On the CGII-C, 1=very much improved and 7=very much worse.

Frequency and percentage of the responses will be summarized by visit for CGII-C and CGII-P separately. The analysis will be conducted by cohort separately. A subject data listing will be provided.

6.3 ANALYSIS OF MONTHS 1 – 3

In order to explore early signals of efficacy, the seizure and cluster analyses described above will be repeated using just the first 3 months of the post-baseline period, defined as the first 90 days following the first day of treatment (Study Days 2 to 91).

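### SAP 6.2.2 calculates the percent change in cluster frequency by subtracting baseline seizure frequency instead of baseline cluster frequency

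*SAP*

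**What the plan says.** SAP 1.2.2 lists as its second secondary endpoint "Percent change in cluster frequency per 28-day period from baseline". SAP 6.2.2 defines the post-baseline rate and then the matching baseline rate: "Baseline 28-day cluster frequency will be calculated as the total number of clusters in the baseline period", divided by days with cluster count data and scaled to 28 days. It then forms the percent change as "post-baseline 28-day cluster frequency minus baseline 28-day seizure frequency) divided by baseline 28-day cluster frequency", times 100%. The baseline cluster rate just defined appears only in the divisor.

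The subtracted term carries the same label as the baseline term in the SAP 6.1 formula. In 6.1 it stands for the total: "Frequency of total seizures includes all seizure subtypes presented as individual seizures or clusters". SAP 6.2.1 treats individual seizure frequency, without clusters, as a separate quantity.

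SAP 6.2.2 also sets out what is reported: "Summary statistics for the baseline and post-baseline values and the arithmetic and percent changes will be presented by cohort". SAP 6.3 extends the calculation to an early window: "the seizure and cluster analyses described above will be repeated using just the first 3 months of the post-baseline period".

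In SAP 6.2.6 the post-baseline count of seizure-free days is "divided by the number of days with available individual seizure occurrence data in the period and multiplied by 100", while the baseline count is divided by days with either individual seizure or cluster data. SAP 6.2.7 has the same asymmetry: cluster data only post-baseline, either kind of data at baseline.

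**The concern.** A percent change needs the same baseline quantity in the numerator and the divisor. SAP 6.1 and 6.2.3 follow that pattern and 6.2.2 does not. SAP section 11, which lists departures from the protocol and the prior SAP, mentions nothing that would make the difference deliberate.

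The subjects affected are those with both clusters and individual seizures at baseline. The protocol's introduction describes clusters as the hallmark of PCDH19 epilepsy and adds: "Patients with PCDH19-FPE may experience individual seizures in addition to clusters and multiple seizure types". For such a subject, on the 6.1 meaning, the formula overstates the reduction in clusters and can show an increase as a reduction. Cohorts were planned at up to 10 subjects (SAP 1.3.3) and are summarised by mean, SD, median, minimum and maximum, so a few distorted values could dominate a cohort summary.

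**Working it through.** The plan states no numerical result for this endpoint, so there is no figure to reproduce. The check evaluates the formula as written against the endpoint as named. All subject counts below are assumed, per 28 days.

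**Notation.** C0 and C1 are baseline and post-baseline cluster frequency (6.2.2). I0 is baseline individual seizure frequency (6.2.1). Baseline total seizure frequency is I0 + C0 (6.1). C0 is above zero, and the same diary days are taken to underlie both baseline rates.

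**Endpoint as named:** 100 × (C1 − C0) / C0.

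**As written, 6.1 meaning:** 100 × (C1 − (I0 + C0)) / C0 = 100 × (C1 − C0) / C0 − 100 × I0 / C0.

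The error is −100 × I0 / C0 percentage points. It is zero only when I0 = 0.

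| C0 | I0 | C1 | As written | Correct |
|---|---|---|---|---|
| 4 | 0 | 4 | 100 × (4 − 4)/4 = 0% | 0% |
| 4 | 1 | 4 | 100 × (4 − 5)/4 = −25% | 0% |
| 4 | 1 | 2 | 100 × (2 − 5)/4 = −75% | −50% |
| 4 | 1 | 5 | 100 × (5 − 5)/4 = 0% | +25% |
| 4 | 10 | 4 | 100 × (4 − 14)/4 = −250% | 0% |
| 2 | 8 | 4 | 100 × (4 − 10)/2 = −300% | +100% |

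The last two results fall below −100%, which is impossible for a percent change in a count rate.

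**As written, individual seizures only:** 100 × (C1 − I0) / C0. This is right only when I0 = C0, and the error can go either way. With C0 = 4 and C1 = 4 (true change 0%), I0 = 2 gives 100 × (4 − 2)/4 = +50%, and I0 = 10 gives 100 × (4 − 10)/4 = −150%. Neither reading gives the endpoint in general.

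**Denominators in 6.2.6 (minor).** Take 100 days with either kind of data, 20 days with individual seizures, k days with cluster data but no individual seizure data, and no true change between periods.

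- k = 0: 80/100 in both periods, difference 0.
- Cluster-only days not classed as seizure free: k = 5 gives 75/100 at baseline and 75/95 = 78.9% post-baseline, +3.9 points. k = 10 gives 70/100 and 70/90 = 77.8%, +7.8 points.
- Cluster-only days classed as seizure free at baseline but left out post-baseline: k = 5 gives 80/100 and 75/95, −1.1 points. k = 10 gives 80/100 and 70/90, −2.2 points.

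The documents do not report whether such days exist.

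**Denominators in 6.2.7 (minor).** The SAP counts a blank cluster entry on a day with seizure data as cluster free. Applied to the denominator too, that rule makes the two periods agree, so there is no numerical effect and only the wording needs alignment.

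**The case against.** The strongest reply is that this is an obvious one-word slip. The section heading, both preceding definitions, the divisor and the opening of the same sentence all point to cluster frequency, and a competent programmer would probably have read it that way. If the text were followed literally, the baseline, post-baseline and arithmetic-change summaries beside it would disagree with the percent change, and a value such as −300% would expose itself. All of this stands as a limit on the likely harm. It does not make the written rule correct: smaller errors such as −25% in place of 0% are not impossible values, and if the program silently departed from the text, the SAP does not document what was done.

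The reach is also narrow. SAP section 11 restricts the per-protocol analysis to the primary endpoint, and cluster frequency is not among the extension tables that SAP section 9 names. On the listed outputs, the problem is confined to the 26-week MITT analysis and its 90-day repeat. That stands.

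The direction of error depends on what the subtracted term means. The bias toward apparent benefit follows from the 6.1 meaning, which is the better reading because the label is identical. On the individual-only reading the sign can reverse.

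Finally, the documents give no baseline mix of individual seizures and clusters for any cohort, so the number of subjects affected is unknown, and the 6.2.6 figures rest on assumed diary patterns. Those two denominator points are consistency edits and do not carry the main finding.

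**Conclusion.** The concern holds. As written, SAP 6.2.2 does not calculate secondary endpoint 2. On the 6.1 meaning, the error per subject is −100 times the ratio of baseline individual seizures to baseline clusters: 25 points at a ratio of 1 to 4, and 400 points at 8 to 2. The algebra does not depend on the assumed counts, but the illustrated sizes do. No effect on reported results can be shown, because the documents do not reveal the programming. The text should be corrected because it is the stated rule for a named endpoint and for its 90-day repeat. The conclusions from the primary and responder analyses are not touched.

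**What to change.** - **6.2.2:** in the subtracted term, replace the word seizure with cluster, so that the baseline cluster frequency already defined there is used in both the numerator and the divisor.
- **Programs:** check the delivered program line for this endpoint and its 6.3 repeat against the corrected text. Include the PCDH19 analysis that SAP section 11 says was run after the 26-week period, if it reported this endpoint.
- **6.2.6 (minor):** use days with available individual seizure data as the denominator in both periods. Using days with either kind of data in both periods, as 6.2.5 does, would also be consistent, provided the SAP says how cluster-only days are classed.
- **6.2.7 (minor):** use days with either kind of data in both periods, as the rule for blank cluster entries already implies.

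The cost is one word, one program check with its repeat, and one denominator phrase in each of the two minor items. No new data or design change is needed.
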